All study assessments will be programmed in the electronic medical record (Epic EMR) with the help of the epic physician builder who is co-investigator on the study ([name] [name], MD). Demographics, key comorbidities (cardiovascular disease, hypertension, diabetes, obesity, osteoporosis, thromboembolic disease, cancer), routine laboratories including inflammatory markers, and disease characteristics will be updated **at every visit**. Information that does not change such as disease onset for psoriasis and psoriatic arthritis will be recorded only at baseline. Study visits will occur at 3-4 month intervals in conjunction with clinical care. Disease assessments will comprise physician assessments (Table 1 a,b), laboratories (Table 2), and patient reported outcomes (Table 3 a,b). Medication doses and changes in medications will be recorded longitudinally. Disease activity measures will be programmed in the medical record such that scores are automatically generated from the primary data elements as illustrated in Table 4.

Table 1a. Physician assessments

PsA Phenotype smartform	Elements
CASPAR classification criteria (cumulative)	Psoriasis (active, history, family history), Nail psoriasis, Dactylitis, Negative rheumatoid factor, Juxtaarticular new bone (radiographic PsA)
Extraarticular manifestations (cumulative)	Uveitis, Inflammatory bowel disease, Inflammatory back pain, Psoriasis type (plaque, pustular, inverse, guttate, erythrodermic) and special locations (scalp, palmoplantar, intergluteal cleft/perianal), Elevated CRP
Comorbidities (from problem list)	Cancer of skin (not melanoma), Melanoma skin cancer, Cancer other than skin (fill in), Coronary artery disease, Diabetes, Fatty liver disease, Obesity , Osteoporosis, Stroke, Thyroid disease, Vitiligo

Table 1b. Disease activity measures

Psoriatic arthritis areas/domains	Physician assessments
Musculoskeletal Arthritis	Tender/swollen joint counts 66/68
Dactylitis	Dactylitis index (LDI basic) (0-20)
Enthesitis	Enthesitis index (SPARCC) (0-18)
Spondyloarthritis	Antropometrics (Cervical range of motion anteroposterior and lateral: occiput to wall, degrees lateral rotation; Thoracic expansion; Lumbar spine: Schober 10 and 15 cm, Lateral lumbar flexion)*

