Skin and nails	Psoriasis body surface area affected (BSA%); Psoriasis location (scalp, upper extremities, lower extremities, torso, abdomen); Psoriasis phenotype (plaque, pustular, inverse, guttate, erythrodermic) Investigator global assessment (0-4); Nail disease (pitting, onycholysis, and surface area affected)

* assessed only at baseline

Table 2. Laboratory assessments

Psoriatic arthritis areas/domains	Laboratory test
Inflammatory markers	C reactive protein (CRP, mg/dL), ESR

We will also assess complete blood counts and comprehensive metabolic panel at every visit as part of usual clinical care. We will retrospectively abstract serologic information collected as part of usual clinical care from the medical record (rheumatoid factor, anti-cyclic citrullinated peptide (anti-CCP) status, HLA-B27, and ANA).

Table 3a. Patient reported treatment success impression

The final questions will be refined with patient research partners to make sure these are formulated such that patients understand we are assessing at each visit whether they have achieved their personal treatment goals for their psoriatic arthritis.

Patient impression of PsA treatment goals met	Response options
1. "Today, considering the level of control of your psoriatic arthritis and psoriasis, do you consider your treatment has been successful?"	1. yes 2. no
2. "If in your opinion, psoriatic arthritis and psoriasis treatments have NOT been successful for you, please choose the three most important manifestations and life impact aspects that are still active for you (from your psoriatic arthritis and psoriasis)."	1. inflamed joints, 2. inflamed tendons, 3. back/spine inflammation, 4. skin psoriasis, 5. nail psoriasis, 6. scalp psoriasis, 7. Pain, 8. Fatigue, 9. Stiffness, 10. Ability to be physically active/exercise, 11. Ability to participate with family activities, 12. Ability to work, 13. Ability to participate in social activities, 14. Emotional impact, 15. Ability to be independent in my daily activities, 16. Other, please fill in.

Patient impression of PsA treatment goals met	Response options
3. Patient acceptable symptom state: "If you were to remain for the next few months as you were during the past week, would this be acceptable or unacceptable for you?"	1. acceptable 2. unacceptable

Table 3b. Patient reported outcomes for disease status and life impact

Psoriatic arthritis areas/domains	Patient reported outcomes

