Safety assessments: All adverse events (AE) will be recorded and managed per usual clinical care. Serious adverse events (SAE) are defined as adverse events that meet any of the following criteria: result in death; are life-threatening (i.e., in the opinion of the Investigator(s) the subject is at immediate risk of death from the AE); require inpatient hospitalization or prolongation of existing hospitalization; result in persistent or significant disability/incapacity (a substantial disruption of the subject's ability to conduct normal life functions); represent a congenital anomaly/birth defect; constitute an important medical event. As part of usual clinical care, some patients participating in the study will be taking apremilast. Any SAE due to apremilast must be reported immediately (i.e., within 24 hours of the Investigators' knowledge of the event) to Amgen Inc Safety by facsimile. A written report (prepared by the Investigator(s) using an SAE Report Form or a 3500A Medwatch form is to be faxed to Safety (see below for contact information).

Amgen Inc Drug Safety Contact Information:

Amgen Inc Corporation
Global Drug Safety and Risk Management
[name]
[name]
[contact]
E-mail: [contact]

Pregnancies: Pregnancies and suspected pregnancies (including a positive pregnancy test regardless of age or disease state) of a female subject or the female partner of a male subject occurring while the subject is on apremilast, or within 30 days of the subject's last dose of study drug, are considered immediately reportable events. Apremilast is to be discontinued immediately. The pregnancy, suspected pregnancy, or positive pregnancy test must be reported to Amgen Inc Safety immediately facsimile using the Pregnancy Report form provided by Amgen Inc.

5. Inclusion/Exclusion Criteria

Inclusion criteria: English speaking/reading adults, ages 18 to 95 years who are patients in the Johns Hopkins Arthritis Center and/or the Psoriatic Arthritis Clinical Program (PI, [name] MD MHS directs the PsA program) and are followed every 3-4 months. Participants have to meet CASPAR classification criteria for psoriatic arthritis (supplementary material), and be able to interact with touch screen computer.

[figure not shown]
Exclusion criteria: None

6. Drugs/ Substances/ Devices – Not Applicable

7. Study Statistics

Grouping of treatment goals met or not met is based on the primary outcome at each study visit (Fig1).

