Figure 1. Determining patient status in terms of treatment goals met (treatment has been successful from the patient's perspective) or not.

a. Predictors of successful treatment/reaching PsA treatment goals (primary outcome) from a patient perspective: In the longitudinal dataset with up to three visits per participant, we will examine predictors of 'treatment goals met' status using logistic regression with covariates disease characteristics and patient reported variables. We will identify predictors associated with a transition state from unmet to met, a stable status of treatment goals met, as well as predictors of stable status of unmet goals or transition in the negative direction (state variable with 4 categories: unmet to met, stable met, stable unmet, met to unmet). Full visits for this study must be in-person so that the physician assessment of the patient's disease is complete.

b. Prevalence of patients reporting successful treatment/they meet PsA treatment goals from their perspective: We will perform exploratory data analysis to estimate the prevalence of 'patient treatment goals met' status in this longitudinal guideline based therapy cohort. We will then compare characteristics of 'treatment goals met' vs 'not met' patient groups using proportions for binary/categorical (chi square tests) and means for continuous variables (t-tests).

c. Frequency and direction of longitudinal transitions between treatment goals met(successful treatment)/not met states: 3 observations/participant Inperson Visits only: We will determine how patient states change over time to define stability of the notion of successful treatment. Interim Telemedicine visit data will be collected to fill gaps between extended in-person intervals.

d. Score ranges that correspond to a status of patients' treatment goals are met (successful treatment) on a set of PsA outcome measures used in the study, including composite disease activity measures: We will calculate average score ranges for multiple variables of interest that correspond to a status of successful treatment for patients.

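### Section 7a fits logistic regression to up to three visits per patient and names no method for within-patient correlation, so standard errors for stable predictors can be too small

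*Combined protocol and SAP*

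**What the plan says.** The opening of Section 7 sets the unit of the outcome: "Grouping of treatment goals met or not met is based on the primary outcome at each study visit". Section 7a then gives the primary model: "In the longitudinal dataset with up to three visits per participant, we will examine predictors of 'treatment goals met' status using logistic regression". Its covariates are described only in general terms: "using logistic regression with covariates disease characteristics and patient reported variables".

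Section 7a also introduces a "state variable with 4 categories: unmet to met, stable met, stable unmet, met to unmet". It names no separate model for this variable and does not say which pair of visits defines a transition.

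Some candidate covariates cannot change between visits, or hardly do:

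- Section 4: "Information that does not change such as disease onset for psoriasis and psoriatic arthritis will be recorded only at baseline".
- Table 1a: CASPAR and extra-articular items are recorded cumulatively.
- Table 1b footnote: the spinal measurements are "assessed only at baseline".
- Text under Table 2: "We will retrospectively abstract serologic information collected as part of usual clinical care from the medical record".

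No section mentions GEE, mixed or conditional models, patient-clustered variance, or an analysis limited to one visit per patient.

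**The concern.** Ordinary logistic regression takes its standard errors from the assumption that rows are independent given the covariates. Here up to three rows come from one person answering the same yes/no question at intervals of 3-4 months. The plan itself expects some persistence, since two of its four states are stable ones.

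If status remains positively correlated within a patient after adjustment, three visits carry less information about a patient-level characteristic than three different patients would. Confidence intervals for such characteristics are then too narrow and p-values too small. The primary objective is to name predictors and adverse predictors of treatment success, so variables could be reported as predictors on weaker evidence than stated.

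**Working it through.** **Inputs.** From the documents: up to three visits per participant, a binary outcome set at each visit, and logistic regression as the method. The documents state no significance level, sample size or within-patient correlation, so there is no planned figure to reproduce. Assumed below: a nominal two-sided 5% test and a range of residual correlations.

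**Formula.** Let m be visits per patient, ρ the within-patient correlation of status left after the covariates, and ICC_x the predictor's own within-patient correlation (1 if fixed; 0.6 taken as largely stable).

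- Design effect: DE = 1 + (m − 1) × ICC_x × ρ
- Reported SE / true SE = 1/√DE
- True error = 2 × [1 − Φ(1.96/√DE)]

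Example: m = 3, ICC_x = 1, ρ = 0.3. DE = 1 + 2 × 0.3 = 1.6; 1/√1.6 = 0.79, so the SE is 21% too small; the true error is 2 × [1 − Φ(1.55)] = 12.1%.

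| Residual ρ | 0.05 | 0.1 | 0.2 | 0.3 | 0.5 | 0.7 |
|---|---|---|---|---|---|---|
| Fixed predictor, 3 visits: SE understated by | 5% | 9% | 15% | 21% | 29% | 35% |
| Fixed predictor, 3 visits: true error | 6.2% | 7.4% | 9.8% | 12.1% | 16.6% | 20.6% |
| Fixed predictor, 2 visits: true error | 5.6% | 6.2% | 7.4% | 8.6% | 11.0% | 13.3% |
| Largely stable predictor, 3 visits: true error | 5.7% | 6.4% | 7.8% | 9.3% | 12.1% | 14.8% |

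**Do the covariates absorb the correlation?** This was simulated with a random-intercept logit, three visits, a null fixed predictor and one strong visit-varying covariate (log-odds 2 per SD, own ICC 0.7). There were 150 or 300 patients and 6,000 runs per setting; all these inputs are assumed.

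| Intercept SD | 0 | 0.5 | 1 | 1.5 | 2 | 3 |
|---|---|---|---|---|---|---|
| Raw correlation of status | 0.26 | 0.28 | 0.32 | 0.37 | 0.42 | 0.52 |
| Residual correlation | 0 | 0.03 | 0.12 | 0.22 | 0.33 | 0.48 |
| Error, covariate in model | 4.6-5.3% | 5.6-5.9% | 8.1-9.2% | 10.4-10.9% | 13.2-14.2% | 16.0-16.3% |

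The formula agrees: at ρ = 0.48, DE = 1 + 2 × 0.48 = 1.96, √DE = 1.4, and 2 × [1 − Φ(1.4)] = 16.2%. So the residual correlation matters, not the raw one.

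Across the same intercept SDs, lowest to highest:

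- weaker covariate (log-odds 1 per SD): 5.0% to 17.0-17.1%;
- largely stable predictor (ICC 0.6), 150 patients: 5.0% to 11.8%;
- incomplete follow-up (60% of patients with three visits, 25% two, 15% one), 150 patients: 5.2% to 14.7%;
- the adjusted model with patient-clustered variance: 4.9-6.5% in all settings.

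**Direction by type of predictor.** A second simulation (200 patients, three visits, 1,500 runs, no other covariate) used status correlations of about 0.22 and 0.43.

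| Predictor | Error at 0.22 | Error at 0.43 |
|---|---|---|
| Fixed within patient | 9.7% | 14.3% |
| Largely stable (correlation 0.7) | 9.8% | 11.6% |
| Uncorrelated across visits | 5.3% | 5.5% |

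For a predictor varying only within patients, at 0.43, the ordinary SE was too large (0.101 against a true 0.078) and the error was 0.9%.

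**Four-category state.** If consecutive visit pairs are used (an assumption), a patient with three visits gives 3 − 1 = 2 records and the same gap applies. With one pair per patient it does not.

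**The case against.** The plan says logistic regression in longitudinal data. It does not say ordinary logistic regression, and GEE and random-intercept models are forms of logistic regression too. That is true, and the plan does not rule them out. But it does not call for them either, and the method it names, applied to the dataset it names, assumes independence.

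Section 4 also says that disease characteristics are refreshed at every visit, and most activity and patient-reported measures can change. No list says which fixed items will enter the model. This limits how many predictors are affected, but it does not remove the problem: disease onset is fixed, and other disease characteristics are recorded once or cumulatively.

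The covariates could absorb all the correlation, in which case nothing is wrong. This stands, but the plan neither checks nor ensures it.

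The error can also run the other way: predictors that vary only within a patient get standard errors that are too large and may be missed. This stands too, and clustered variance corrects it as well.

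Finally, uncorrected robust variance is somewhat liberal with few patients: error for a stable predictor was 7.3-7.6% at 40 patients and 5.3-5.7% at 150 in simulation. That is a refinement of the remedy, not a reason to leave the model as it is.

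**Conclusion.** The concern holds. As written, Section 7a does not account for repeated visits by the same patient. For predictors that are fixed or largely stable within a patient, its standard errors are too small whenever status stays positively correlated after adjustment. At an assumed nominal 5%, the simulated error for a fixed predictor over three visits runs from nominal, with no residual correlation, to about three times nominal at a residual correlation near 0.5. The documents do not allow the size to be fixed more closely. Visit-level point estimates are not affected; intervals and p-values are. Because these decide which predictors are reported for the primary objective, the text should be corrected before the analysis.

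**What to change.** In Section 7a, write: *Treatment goals met status will be modelled by logistic regression using GEE with working independence and robust variance clustered on patient.* If the number of patients turns out small, add a small-sample correction to the robust variance. Use a random-intercept logistic model instead only if patient-specific odds ratios are the stated target.

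For the four-category state, say which pair of visits defines a transition. If a patient can contribute more than one, use multinomial logistic regression with patient-clustered variance.

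If 7b or 7e pools visits or changes within a patient, apply the same clustering or resample by patient. If each uses one record per patient, say so; nothing else is then needed.

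The cost is a few lines of text and standard software, with no new data. Where residual correlation exists, intervals for stable predictors will widen. Working independence may lose some efficiency for visit-varying predictors.

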Psoriatic arthritis (PsA) is a heterogeneous autoimmune disease that occurs in one in three people with the skin disease psoriasis. PsA can cause arthritis (joint inflammation), enthesitis (tendon and ligament inflammation), sausage digits (swollen entire finger or toe), spondyloarthritis (spinal inflammation). Skin involvement by psoriasis is also highly variable in terms of psoriasis type and location. Through combined skin and musculoskeletal involvement, psoriatic disease has a significant life impact with decrease quality of life including uncomfortable symptoms, ability to participate in life and functioning. Medications used to treat PsA have sometimes an uneven effect on the various PsA manifestations where some are more effective for skin while others more effective for the joints. In this context, clinical care and treatment of PsA is a complex process which balances disease activity with medication risks and benefits as well as patient priorities. Professional PsA treatments guidelines state that PsA treatment goals are disease remission or low disease activity. Several studies to date have shown that physicians tend to overestimate remission and low disease activity in PsA patients when compared to disease activity indices. Also patients and physicians frequently do not align on perceptions of remission or low disease activity. In the proposed study we aim to identify predictors of successful treatment from a patient perspective on a range of disease measures including psoriasis, arthritis, enthesitis, dactylitis, patient reported outcomes, and laboratory assessments which are routinely collected in the clinical care of PsA. Secondary endpoints are to quantify longitudinally how stable a state of treatment success is from a patient perspective, and to define score ranges for disease measurements, including health-related quality of life measures, that correspond to treatment success from a patient perspective. **The impact of this research is that we will be able to define parameters predictive of achieving treatment success from a patient perspective, which will then inform goals of care for psoriatic arthritis.**

2. Objectives

Primary objective

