To determine predictors of reaching PsA treatment goals/treatment success (primary outcome) from a patient perspective in an academic PsA guideline-based treatment cohort. Conversely, to determine adverse predictors to reaching this desirable state. The primary outcome determination is based on the patients' report of whether they are/are not at goal with their PsA treatment.

Secondary objective(s)

To estimate the following parameters:

- A. Prevalence of patients reporting they met PsA treatment goals (successful treatment) from their perspective.

- B. Frequency and direction of longitudinal transitions between treatment goals/met not met states: 3 observations/participant.
- C. Score ranges that correspond to a status of patients' treatment goals met on a set of PsA outcome measures used in the study, including composite disease activity measures.
- D. On the same set of PsA outcome measures, meaningful change values in patients who transition longitudinally to the better and worse categories.

3. Background

Efficacy of therapeutics in PsA is incomplete, considering at most 60% of patients achieve the primary efficacy outcome in clinical trials. More so, treatment goals from the patient perspective, as well as alignment of patient opinion with index-based definitions of treatment success are part of the knowledge gap in PsA. In clinical practice, desirable treatment targets have been defined by experts as Disease Activity in Psoriatic Arthritis (DAPSA) low disease activity or remission, or Minimal Disease Activity (MDA)2. The clinical DAPSA score is computed by adding the sum of tender (out of 68) and swollen (out of 66) joints with patient global assessment and patient reported pain (each on a scale of 0-10). DAPSA remission state is defined by a score≤ 4, and DAPSA low disease activity as ≤ 14. MDA is a checklist based state defined as achieving five out of the following seven criteria: ≤ 1 swollen joint, ≤ 1 tender joint, ≤ 1 tender enthesal point, HAQ-DI score ≤ 0.5 (range 0-3), patient reported pain ≤ 1.5, patient global assessment ≤ 2, body surface area psoriasis ≤ 3%. It is of great interest to ascertain if guideline-based PsA clinical care achieves individual patient goals as articulated by patients, and to identify predictors of achieving individual patient goals from PsA treatment.

4. Study Procedures

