Musculoskeletal	Bath Ankylosing Spondylitis Disease Activity Index (BASDAI)
Health related quality of life	Psoriatic Arthritis Impact of Disease (PsAID12, PsA specific) PROMIS Profile 29 (generic)
Pain	Pain visual analog scale (VAS, 0-100 mm) PROMIS Pain interference (Profile 29)
Physical function	PROMIS Physical Function 10
PsA patient globals	Patient global Arthritis (GRAPPA) (VAS, 0-100 mm) Patient global Psoriasis (GRAPPA) (VAS, 0-100 mm)
Fatigue	PROMIS Fatigue 8a
Participation, Depression, Anxiety Sleep quality	PROMIS Profile 29

Table 4. Disease activity measures (programmed in EMR and calculated automatically from elementary data)

Disease activity measure	Components and calculation
Disease Activity Psoriatic Arthritis (DAPSA) Cutoffs Remission \leq 4 Low $4 \leq 14$ Moderate $14 \leq 28$ High ≥ 28	Tender/swollen joint counts: 68/66 Patient global (0-10) Patient pain (0-10) C reactive protein (mg/dL) DAPSA = 68tender joints + 66swollen joints + patient global + pain + CRP (ranges from 0 to more than 154) Clinical DAPSA = 68tender joints + 66swollen joints + patient global + pain (0-154)
Very low disease activity (VLDA) and Minimal disease activity (MDA) VLDA (7/7 criteria met) MDA (5/7 criteria met)	Set of 7 criteria: 1. Tender joint count $68 \leq 1$ 2. Swollen joint count $66 \leq 1$ 3. Patient global $\leq 2/10$ 4. Pain $\leq 1.5/10$ 5. Health assessment questionnaire disability index ≤ 0.5 6. Enthesitis ≤ 1 7 Body surface area psoriasis $\leq 3\%$

Patients will be enrolled in CRMS and the CRMS study flag in Epic will be used to identify patients for research visits and data extraction. The unique study identifier will be linked to the patients' JHH medical record number and only study staff will have access to the key table. This will allow study staff to keep track of enrollment and study visits and to specify data query parameters to the EPIC team at the stage of data extraction. If the patient signs consent and has a study visit on the same day, the CRMS flag will not be available to trigger specific Epic content, since the update from CRMS to EPIC takes about 24 hours. Because of this, we will institute a patient-level Smartdata element in Epic that will be flagged after the patient signs consent. This will also indicate inclusion in the study and can be used to trigger specific Epic content for the visit.

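### Section 7a puts disease measures and patient-reported scores into the logistic regression without separating them, so coefficients for joints, entheses, dactylitis and skin may be attenuated and misread

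*Combined protocol and SAP*

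**What the plan says.** The primary objective in Section 2 is "To determine predictors of reaching PsA treatment goals/treatment success (primary outcome) from a patient perspective", and also to find adverse predictors. The outcome is the yes/no answer to Table 3a, question 1: "do you consider your treatment has been successful". Section 7a analyses it "using logistic regression with covariates disease characteristics and patient reported variables". The plan gives no blocks, order of entry, selection rule or collinearity rule.

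The candidate variables fall into two families:

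- **Physician-assessed and laboratory measures** (Tables 1b and 2): "Tender/swollen joint counts 66/68", the SPARCC enthesitis index, the dactylitis index, psoriasis body surface area, CRP and ESR.
- **Patient-reported measures** (Table 3b): pain, separate patient globals for arthritis and for psoriasis, PsAID12, and PROMIS measures of function, fatigue and mental health.

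The opening abstract names patient-reported outcomes among the candidate predictors. It describes the intended use as follows: "we will be able to define parameters predictive of achieving treatment success from a patient perspective, which will then inform goals of care".

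**The concern.** The two families are plausibly successive steps on one path. Active joints, entheses and skin cause symptoms; patients rate those symptoms on the pain, global and impact scales; and the same patients then say whether treatment has succeeded. If the ratings are held fixed, the coefficient for a disease domain loses whatever part of its association runs through them. A larger sample, shrinkage or better standard errors would not change this, because the coefficient answers a different question.

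What is at stake is interpretation. The results are meant to inform goals of care, so individual coefficients will be read. A coefficient near zero for skin or joints could be taken to mean that the domain is unimportant to patients. It would in fact mean that the domain adds little once the patient's own rating is known.

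**Working it through.** The documents give no sample size, prevalence, correlations or effect sizes, so there is no planned figure to reproduce. The mechanism can only be illustrated, and every numerical input below is an assumption.

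**Large-sample illustration** (n = 200,000, one observation per patient). J, S and E are independent standardised joint, skin and entheseal domains, with higher values worse.

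- Global/pain score: G = a·J + b·S + c·E + noise, with total variance 1.
- Impact score: Q = 0.8·G + 0.6·noise.
- Success: logit P = 0.3 − 1.0·G − 0.3·Q − direct effects.

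Model 1 contains J, S and E. Model 2 adds G and Q. Odds ratios are per SD worse.

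| Assumption | Model 1 (J / S / E) | Model 2 (J / S / E) |
|---|---|---|
| Loadings 0.6, 0.4, 0.3; no direct effect | 0.52 / 0.64 / 0.72 | 1.00 / 1.00 / 1.00 |
| Loadings halved; direct log-odds −0.5 for each domain | 0.50 / 0.54 / 0.58 | 0.61 / 0.60 / 0.61 |
| Loadings zero (no mediation); direct log-odds −0.5 for each domain | about 0.68 each | about 0.60 each |

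Reading the rows:

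1. In the first row the domains explain 0.36 + 0.16 + 0.09 = 0.61 of the variance of G. The direct effects were set to zero, so Model 2 must return exp(0) = 1.00. The row shows the extreme case and does not estimate what this study would find.
2. In the second row the explained share is 0.09 + 0.04 + 0.0225 = 0.1525. Model 2 recovers the direct effect, exp(−0.5) = 0.61. The domains are attenuated but still clearly visible.
3. In the third row nothing is mediated, yet the odds ratio still moves, and it moves away from 1. This is non-collapsibility: adding a strong predictor changes a logistic odds ratio even when that predictor is unrelated to the domain. A change in odds ratio between models therefore does not measure the mediated share.

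**Smaller-sample illustration** (assumed n = 200, 400 replicates, two-sided 0.05). One standardised domain X has correlation r = 0.3 / 0.5 / 0.7 with one patient score M.

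- Effect entirely through M (log-odds 1.5 per SD of M): the odds ratio for X goes from 0.72 / 0.56 / 0.41 without M to 0.99 / 1.00 / 0.99 with it. The share of significant results falls from 61% / 98% / 100% to 2% / 4% / 4%.
- Partly direct (1.2 through M, 0.3 direct): the odds ratio goes from 0.58 / 0.47 / 0.36 to about exp(−0.3) = 0.74. Power falls from 96% / 100% / 100% to 38% / 35% / 26%.
- M without effect on the outcome (direct log-odds 0.8 for X; r = 0, 0.3 or 0.5): the odds ratio is 0.44 to 0.45 in both models. Masking needs the patient score to carry part of the effect.

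Both illustrations ignore correlation between visits of the same patient.

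**The case against.** Four points can fairly be made for the plan.

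- **7a does not literally say that everything enters one simultaneous model.** It names a method and two families of covariates, and the same paragraph also plans an analysis of a four-category transition state. This stands. The combined model is the natural reading and not an explicit statement. If separate models are intended, the text still needs to say so.
- **Patient-reported outcomes are intended predictors, and no total causal effect is named as the target.** This also stands. A reader might infer that the combined model is simply wrong. The documents do not support that, since it is a legitimate model for independent prediction. The trouble arises only when its domain coefficients are read as the whole importance of a domain.
- **Section 7b compares the met and not-met groups by chi-square and t-tests, and 7d gives score ranges for patients at goal.** These would show marginal differences and reduce the risk of a misreading. They do not remove it: 7b is exploratory, serves a secondary objective, and adjusts the domains neither for one another nor for demographics.
- **The near-null figures are built in by assuming no direct effect.** Correct. A reader might infer that the study will report joints and skin as irrelevant, but nothing in the documents establishes that.

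A reader might also infer that the acceptable-state question ("would this be acceptable or unacceptable for you") will be a covariate. Nothing says so. It sits in Table 3a with the outcome question, apart from the patient-reported outcomes in Table 3b.

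**Conclusion.** The point holds as a matter of specification and interpretation. Under the natural reading of 7a, the coefficients for joints, entheses, dactylitis and skin are conditional on the patient's own ratings, and the plan neither says so nor provides an adjusted model without those ratings. Attenuation follows to the extent that the domains act through symptoms. That is plausible from what the scales ask, but the documents do not demonstrate it.

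The size is unknown. Under the assumptions shown, the result ranges from complete masking to a moderate shift in which the domains remain evident. The combined model should stay, labelled for what it estimates, with a disease-domain model beside it.

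**What to change.** In Section 7a, prespecify two models and report both:

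1. Demographics, disease history and physician-assessed or laboratory domains. Use this model to interpret the disease predictors. Composites such as DAPSA and MDA stay out of it, because they combine joint counts with patient global and pain.
2. Model 1 plus the patient-reported variables of Table 3b. Use this model for independent prediction.

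Add three statements:

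- A domain's coefficient in model 2 is conditional on the patient's own ratings and is not evidence that the domain does not matter.
- The models will be compared by average marginal effects (differences in predicted probability). The change in odds ratio will not be read as the mediated share.
- PASS (Table 3a, question 3) is not a covariate.

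The cost is a paragraph of plan text, one extra model and one extra table, all on data already planned for collection.
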